8.4.3 Pregnancy and assessments of fertility

A condom is required for all sexually active male subjects to prevent them from fathering a child AND to prevent delivery of study treatment via seminal fluid to their partner. In addition, male subjects should not donate sperm for the time period specified above.

All women enrolled in the study will have pregnancy testing regardless of fertility status. See the Assessment schedule ([Table 8-1](#)), for timing of the protocol-required pregnancy testing; additional pregnancy testing may be performed to meet local requirements. A positive urine pregnancy test requires immediate interruption of study treatment until serum β -hCG is performed and found to be negative.

Refer to [Section 10.1.4](#) for details on Reporting Pregnancy.

Assessments of Fertility

Refer to [Section 5.2](#) for criteria to identify women who are not of childbearing potential.

Medical documentation of oophorectomy, hysterectomy, or tubal ligation must be retained as source. Subsequent hormone level assessment to confirm the woman is not of childbearing potential must also be available as source documentation in the following cases:

- Surgical bilateral oophorectomy without a hysterectomy
- Reported 12 months of natural (spontaneous) amenorrhea with an appropriate clinical profile.

In the absence of the above medical documentation, FSH testing is required of any female subject, regardless of reported reproductive/menopausal status at Screening/Baseline.

8.4.4 Safety follow-up call

All randomized and/or treated subjects will have a safety follow-up call conducted at weeks 32 and 42, with the following objectives:

1. To follow-up on subjects' safety between week 28 and 52, when no site visits are scheduled
2. To collect information on AEs of special interest, SAEs and concomitant medication (NSAID use must be reported as accurately as possible), and COVID-19-related symptoms

Documentation of attempts to contact the subject should be recorded in the source documentation.

8.4.5 Appropriateness of safety measurements

The safety assessments selected are standard for this indication/subject population.

8.4.6 COVID-19 contingency plan

The sponsor recommends that subjects in the study are screened for asymptomatic carriage of SARS-CoV-2 within 1 week prior to first dosing. Adequate viral testing availability and turnaround is required for site participation. SARS-CoV-2 testing should always be performed as per national regulatory requirements or guidelines in participating countries.

Any subject that presents COVID-19-related symptoms, in the opinion of the investigator, and/or has a positive SARS-CoV-2 PCR or antigen test within 1 week prior to first dosing will not be enrolled in the study until the infection has resolved and will receive follow-up medical attention as per local site-specific procedures. The subject may be rescreened. Refer to [Section 8.1](#) for details on screening and rescreening procedures.

Any subject that presents COVID-19-related symptoms, in the opinion of the investigator, and/or has a positive SARS-CoV-2 PCR or antigen test from Day 1 to EoS will receive follow-up medical attention as per local site-specific procedures and follow COVID-19 national guidelines. Where possible, subjects should return for the upcoming assessments indicated in the Assessment Schedule after the subject has a negative SARS-CoV-2 PCR or antigen test. However, each case must be discussed and agreed with the Sponsor on a case-by-case basis.

8.5 Additional assessments

8.5.1 Pharmacokinetics

8.5.1.1 PK blood and synovial fluid samples collection

PK blood collections will be done in all subjects. For details on PK blood collection and processing, labeling and shipment instructions, see SOM.

PK samples will be collected at the time points or collection intervals defined in the Assessment schedule/Sample Log. All samples will be given a unique sample number and a collection number. For plasma, the exact data and time of sampling will be entered on the PK blood collection page of the eCRF by the medical personnel or sent as electronic files. These actual sampling times will be used for determination of PK parameters. Sampling problems will be noted in the comments section of the eCRF.

LRX712 and metabolite MAE344 concentrations will be determined in plasma and synovial fluid using validated LC-MS/MS methods. The anticipated lower limit of quantification (LLQ) for LRX712 and MAE344 will be approximately 25 and 100 pg/mL ng/mL, respectively, for plasma.

A non-validated method will be used for additional metabolite investigations / exploratory work, if required, in line with defined exploratory objectives. Untreated samples (placebo) will not be analyzed. Concentrations will be expressed in mass per volume units and will refer to the free base. Concentrations below the LLQ will be reported as “zero” and missing data will be labeled as such in the Bioanalytical Data Report.

CCI

A large rectangular area of the page is completely blacked out, indicating that the content has been redacted. The redacted area starts below the 'CCI' label and extends down to the bottom of the page, ending with a small white rectangular gap.

8.5.1.2 PK parameters in plasma

For standard PK abbreviations and definitions see the list provided at the beginning of this protocol.

The following plasma PK parameters of LRX712 will be determined using the actual recorded sampling times and non-compartmental method(s) with Phoenix WinNonlin (Version 6.2 or higher): Cmax, Tmax, Cmin from the plasma concentration-time data after multiple intra-articular dose administration of LRX712.

8.5.2 Biomarkers

[figure not shown]
CCI

Sample(s) will be collected at the time point(s) defined in the Assessment Schedule (Table 8-1).

[figure not shown]
Follow instructions for sample collection, numbering, processing, and shipment provided in the laboratory manual.

CCI

8.5.2.1 Additional biomarker assessments

CCI

8.5.2.2 Use of residual biological samples

Residual blood, urine, and synovial fluid samples may be used for another protocol-specified endpoint.

CCI

8.5.2.3 Hypothesis free/Protein profiling

CCI

Serum and synovial fluid samples will be collected at the time points defined in the Assessment schedule ([Table 8-1](#)). Instructions are outlined in the SOM regarding sample collection, numbering, processing and shipment.

Markers to be assessed include but are not limited to profiling proteins.

Detailed descriptions of the assays will be included in the Bioanalytical Data Reports.

8.5.2.4 Soluble biomarkers in circulation

Serum and urine samples will be collected according to the detailed instructions outlined in the SOM.

CCI

The list may be changed or expanded further, as it is recognized that more relevant or novel biomarkers may be discovered during the conduct of the study.

Sample(s) will be collected at the time point(s) defined in the Assessment Schedule ([Table 8-1](#)).

Instructions for sample collection, numbering, processing, and shipment are provided in the laboratory manual and/or SOM.

8.5.2.5 Soluble biomarkers in synovial fluid

Synovial fluid samples will be collected by appropriately equipped and trained staff.

CCI

The list may be changed or expanded further, as it is recognized that more relevant or novel biomarkers may be discovered during the conduct of the study.

Sample(s) will be collected at the time point(s) defined in the Assessment Schedule ([Table 8-1](#)).

Follow instructions for sample collection, numbering, processing, and shipment provided in the laboratory manual and/or SOM.

8.5.3 Synovial fluid volume

CCI

In case of dry

taps, synovial fluid volume will not be calculated in order to avoid joint lavage.

CCI

8.5.5 Knee X-ray

Radiography will serve an important role in assessing and verifying 3 eligibility criteria for adequate subject selection:

1. Kellgren-Lawrence grade to confirm the presence of knee OA of mild or moderate severity (KLG 2 or 3).
2. Joint space width measured at a fixed location ($x=0.225$) in the medial tibio-femoral compartment of the index knee, in the range of 1.5-3.5 (females) or 2 to 4 (males) mm.
3. The anatomic PA axis as assessed by AP weight-bearing short knee radiography, to verify that there is no radiographically meaningful varus or valgus malalignment in the index knee (i.e., ≥ 7.5 degree).

All measurements will be performed locally by qualified staff at the investigational sites or delegated third party staff e.g., at specialized X-ray imaging facilities. For details, please refer to the Imaging Charter.

The following characteristics must be used for Kellgren & Lawrence grading ([Schiphof et al 2008](#)):

Grade 0: no changes

Grade I: possible osteophytes only

Grade II: definite osteophytes and possible joint space narrowing

Grade III: moderate osteophytes and/or definite joint space narrowing

Grade IV: large osteophytes, severe joint space narrowing and/or bony sclerosis

9 Study discontinuation and completion

9.1 Discontinuation

9.1.1 Discontinuation of study treatment

Discontinuation of study treatment for a subject occurs when study treatment is stopped earlier than the protocol planned duration and can be initiated by either the subject or the investigator.

The investigator must discontinue study treatment for a given subject if he/she believes that continuation would negatively impact the subject's well-being.

Study treatment must be discontinued under the following circumstances:

- Subject/guardian decision
- Pregnancy
- Use of prohibited treatment as per recommendations in [Section 6.2.2](#)
- Subject presenting with a SAE that is suspected to be related to LRX712
- At least Moderate or Severe (Grade 2 or 3) local tolerability reaction according to the CTC-AE criteria (causes disability, limits self-care ADL, requires elective operative intervention and thereby hospitalization)
- At least Moderate or Severe (Grade 2 or 3) allergic reaction according to the CTC-AE criteria (results in bronchospasm with or without urticaria, edema/angioedema, hypotension, and it requires parenteral infusion therapy)
- Any protocol deviation that results in a significant risk to the subject's safety
- If a liver or renal event occurs, follow the guidelines outlined in [Appendix 1](#) and [Appendix 2](#) regarding discontinuation of study treatment
- Any laboratory abnormalities that in the judgment of the investigator prevents the subject from continuing participation in the study
- Any situation in which continuing study participation might result in a safety risk to the subject
- Following emergency unblinding

If discontinuation of study treatment occurs, the investigator should make a reasonable effort to understand the primary reason for the subject's premature discontinuation of study treatment and record this information.

Subjects who discontinue study treatment or who decide they do not wish to participate in the study further should NOT be considered withdrawn from the study UNLESS they withdraw their consent (see [Section 9.1.3](#)). **Where possible, subjects who discontinued study treatment should return for the upcoming assessments indicated in the Assessment Schedule. Alternatively, they should return for an EOS visit (CC1**

) for the last safety assessments. If they fail to return for these assessments for unknown reasons, every effort (e.g., telephone, e-mail, letter) should be made to contact the

subject/pre-designated contact as specified in [Section 9.1.4](#). This contact should preferably be done according to the study visit schedule.

If the subject cannot or is unwilling to attend any visit(s), the site staff should maintain regular telephone contact with the subject, or with a person pre-designated by the subject. This telephone contact should preferably be done according to the study visit schedule.

After study treatment discontinuation, at a minimum, in abbreviated visits, the following data should be collected at clinic visits or via telephone/email contact:

- New / concomitant treatments
- Adverse Events / Serious Adverse Events

If discontinuation occurs because treatment code has been broken, please refer to Emergency breaking of treatment code section.

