9.1.5 Study stopping rules

The study will be stopped with no further dosing pending a full safety review, if any of the following criteria are met:

- Two (2) or more subjects presenting with the same SAE (as determined by CTC-AE criteria) that are all deemed as possibly/probably related to LRX712 by the Investigator or the Sponsor's Drug Safety Expert.
- Two (2) or more subjects presenting with a severe local tolerability issue of at least Grade 3 confirmed by the Investigator or the Sponsor's Drug Safety Expert.
- Two (2) or more subjects with acute allergic reaction of at least Grade 3 (as per CTC-AE criteria) following i.a. LRX712 administration.
- Two (2) or more subjects experience acute exacerbation of the knee OA with related intense pain symptoms confirmed by the Investigator or the Sponsor's Drug Safety Expert.
- The Sponsor considers that the number and/or severity of AEs, abnormal safety monitoring tests or abnormal laboratory findings justify putting the study on hold.
- One (1) or more patients presenting with a SADE related to the 7T MRI.

The study may resume following the safety review, if the Investigator and Sponsor agree it is safe to proceed.

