9.1.6 Treatment arm stopping rules

Any of the treatment arms will be paused with no further dosing of that dose level pending a full safety review, if any of the following criteria are met:

- Two (2) or more subjects in the same treatment arm present with moderate or severe injection site AE of warmth and swelling that is deemed as possibly or probably related to LRX712 injection.
- The Sponsor considers that the number and/or severity of AEs, abnormal safety monitoring tests or abnormal laboratory findings justify putting the treatment arm on hold.

In the event that one treatment arm is paused for full safety review, the other treatment arm and the placebo arm will continue as per assessment schedule.

If after the full safety review of the paused treatment arm the Sponsor considers that it needs to be stopped, the study will continue with the placebo arm and the other treatment arm e.g., placebo and 15 mg LRX712.

The study subjects randomized to the stopped treatment arm may continue the study or resume dosing following the safety review, if the Investigator and Sponsor agree it is safe to proceed for them e.g. they did not experienced any of the injection site AEs that led to the discontinuation of study treatment and pausing that treatment arm:

1. In the event any subject has not completed the full dosing regimen (3 doses), he/she will continue the study on the other dose level until completing the full dosing regimen e.g., 15 mg LRX712
2. In the event any subject has completed the full dosing regimen, he/she will continue the study per the assessment schedule

The pending number of subjects that would have been randomized to the stopped treatment arm will be randomized to the other treatment arm e.g., if the 25 mg LRX712 treatment arm was stopped after 5 subjects were randomized to it, then the remaining 10 will be randomized to the 15 mg LRX712 by means of a new randomization list.

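### Protocol 9.1.1 stops dosing at Grade 2 or higher local reactions, but the parenthesis beside that threshold describes events well above moderate and should be removed or replaced

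*Protocol*

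**What the plan says.** Protocol 9.1.1 lists the circumstances in which study treatment must be discontinued. Four entries matter here.

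- Local reactions: "At least Moderate or Severe (Grade 2 or 3) local tolerability reaction according to the CTC-AE criteria", followed in parentheses by "causes disability, limits self-care ADL, requires elective operative intervention and thereby hospitalization".
- Allergic reactions: the same grade wording, followed in parentheses by "results in bronchospasm with or without urticaria, edema/angioedema, hypotension, and it requires parenteral infusion therapy".
- Serious events: "Subject presenting with a SAE that is suspected to be related to LRX712".
- A catch-all: "Any situation in which continuing study participation might result in a safety risk to the subject".

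The section does not say whether the parentheses define, limit or illustrate the grade. Nor does it say whether one listed item is enough or all are needed.

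Two neighbouring sections set the higher-level rules. Section 9.1.5 stops the study for "Two (2) or more subjects presenting with a severe local tolerability issue of at least Grade 3" and for "Two (2) or more subjects with acute allergic reaction of at least Grade 3". Section 9.1.6 pauses an arm when "Two (2) or more subjects in the same treatment arm present with moderate or severe injection site AE of warmth and swelling", if the events are judged possibly or probably related to the injection.

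**The concern.** The bullet gives two thresholds for one mandatory action. The grade puts the floor at moderate. The parenthesis puts it near the level of a serious event. Two sites could follow the same sentence and decide differently about the same swollen knee.

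This matters because local tolerability is the main known risk of the drug. Injection site events at 75 mg led to the hold in February 2021 (Amendment 4 rationale). Each subject is due three injections, so a reaction to the first or second raises a re-dosing decision.

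**Working it through.** **1. The parenthesis against the protocol's own definition of serious.** The documents do not reproduce the CTCAE text, so the comparison uses 10.1.2.1.

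- *Operation with hospitalization.* Inpatient hospitalization makes an event serious. The exception for elective treatment covers pre-existing conditions unrelated to the indication, so it does not cover an operation needed because of an injection reaction.
- *Disability.* 10.1.2.1 requires it to be persistent or significant, whereas 9.1.1 says only disability. The overlap is large but not complete.
- *Limited self-care.* This is not an SAE criterion.

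If the parenthesis governed, the local bullet would add little to the separate SAE bullet beyond limited self-care and lesser disability.

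**2. What each reading does after the first or second injection.**

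| Local reaction | Stated grade | Parenthesis, one item enough | Parenthesis, all items needed |
|---|---|---|---|
| Moderate; no disability, self-care intact, no operation | Stop | Bullet does not apply | Bullet does not apply |
| Grade 2 or higher, self-care limited, nothing else | Stop | Stop | Bullet does not apply |
| Operation and admission | Stop | Stop | Other items also needed, but the SAE bullet stops it if suspected related |

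The first row is the conflict, and it does not depend on how the list is read.

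**3. Which threshold is intended.** Section 9.1.6 acts on moderate or severe injection site events. It lets subjects of a stopped arm resume dosing if, for example, they had none of the injection site AEs that led to discontinuation and to the pause. That ties moderate events to individual discontinuation. Section 9.1.5 says at least Grade 3 where Grade 3 is meant. The rules then form a ladder: a subject at Grade 2, an arm at two moderate or severe warmth-and-swelling events, the study at two Grade 3 local events. If the parenthesis governed, the rule for one subject would be laxer than the rule for the arm.

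**4. The allergic bullet.** The grade wording is the same. The nearest support for a mismatch is the example in 10.1.2.1 of intensively treated allergic bronchospasm as a medically significant event, but the bullet does not mention intensive treatment. Section 9.1.6 does not cover allergy. The Grade 2 reading rests mainly on the bullet's own explicit grade.

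**5. Has the drug caused reactions that the two wordings separate?** The only graded figures are single-dose first-in-human data (Protocol 1.3.1): moderate reactions in 3/4 active subjects at 40 mg and 2/4 at 75 mg. Pooled: (3 + 2)/(4 + 4) = 5/8 = 62.5%, Clopper-Pearson 95% interval 24.5% to 91.5%. All five meet the stated grade. That study reported no SAEs, so if its SAE definition matched 10.1.2.1, none of the five involved admission for the reaction. Whether any limited self-care is not reported.

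**6. What a stop costs the analysis.** Doses fall at Day 1, Week 4 and Week 8; post-baseline MRI falls at Weeks 16, 28 and 52. A subject stopped after the first or second injection misses a dose before any post-baseline scan. SAP 4.1.3 sets aside data after a missed dose, and SAP 4.1.4 requires at least one post-randomization measurement, so that subject contributes nothing to the primary comparison.

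For scale, take the planning inputs (difference 123 mm³, SD 130 mm³, 13 per arm, two-sided 10%). The normal approximation gives power of 77.9% (SAP: 78%) and the t-test 75.8% (Protocol: 75%). With 10 active subjects against 13 placebo, t-test power is 70.2%; with 8 it is 65.0%. These losses are assumed, not forecast, and Protocol 9.1.2 provides for replacement.

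**The case against.** The strongest reply is that the operative rule is already explicit. The bullet names the grade and the grading system, and 10.1.1.1 requires a CTCAE grade for every AE, so the investigator holds the deciding value. The heading also spans Grades 2 and 3, and the parenthesis may describe only the upper end. This has force: the text is not clearly worse than Grade 3. It still cannot describe the Grade 2 floor, and the bullet does not say that it describes Grade 3 alone.

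A reader might infer that nothing protects the first subject with a moderate reaction. The documents do not support that. Section 9.1.1 requires the investigator to stop if continuing would harm the subject's well-being, and it adds the catch-all for any safety risk. Sections 9.1.5 and 9.1.6 also let the sponsor hold the study or an arm on the number or severity of AEs, with no minimum count and no restriction to warmth and swelling. These safeguards are real but rest on judgement, whereas the graded bullet exists to make the stop mandatory.

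A reader might also take 5/8 as the share of subjects at risk here. It comes from single injections of 40 and 75 mg, doses that newly randomized subjects do not receive. Section 1.3.1 describes reactions at lower doses as less frequent and milder. The absence of admissions bears on one item of the list only and relies on an SAE definition that the documents do not give for that study.

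Finally, the allergic case is thin. That stands, and it limits what can be said about that bullet.

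**Conclusion.** The local-reaction bullet contradicts itself and should be corrected. The stated grade is the intended threshold, as 9.1.5 and 9.1.6 indicate, and the parenthesis does not fit its lower end. The consequence is possible re-dosing after a moderate reaction and inconsistent decisions between sites, partly mitigated as described above. For the allergic bullet the conclusion is weaker: the form is the same, and consistency is the main reason to edit it.

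The size at 15 and 25 mg is unknown. No moderate-reaction rate is given for those doses, and it is not known how many investigators would follow the parenthesis. The first-in-human figures show only that this drug has caused reactions on which the two wordings can differ.

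The conclusion rests on the protocol's own SAE definition and stopping rules, not on the CTCAE text. Confidence is medium.

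**What to change.** In the local bullet of Protocol 9.1.1, write *Grade 2 or higher per CTC-AE* and delete the parenthesis, or replace it with wording that fits Grade 2. Make the same edit to the allergic bullet for consistency.

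The drafting cost is two bullets in a protocol amendment. The change adds no stop beyond what the stated grade already requires. If sites would otherwise have followed the parenthesis, however, some more subjects may stop dosing. Each who misses a dose becomes an intercurrent event under SAP 4.1.3 and is subject to replacement under Protocol 9.1.2. The documents do not allow that number to be estimated.
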